3.1.2 Faster-acting insulin aspart

Faster-acting insulin aspart (also called faster aspart) is insulin aspart in a new formulation. Insulin aspart is marketed worldwide as NovoRapid[®] (in US it is NovoLog[®]). In the remainder of this document, the name NovoRapid® will be used. Faster-acting insulin aspart is being developed with the objective of achieving an increased early absorption of insulin aspart compared to NovoRapid® thereby providing a faster insulin action. Faster-acting insulin aspart aims at mimicking the physiological prandial insulin secretion pattern better than currently available treatment and thereby more effectively controlling the PPG excursion and achieving a better PPG control, and increased flexibility in the time of dosing around meals compared with NovoRapid[®]. Results from clinical pharmacology trials in adults comparing pharmacokinetic and pharmacodynamic properties of faster-acting insulin aspart and NovoRapid® have shown that faster-acting insulin aspart elicited an earlier onset of appearance and a greater early exposure to insulin aspart than NovoRapid[®] in Subjects with T1DM, with the largest difference found within the first 15 minutes after injection. Faster-acting insulin aspart also elicited a greater early glucose-lowering effect than NovoRapid[®]. but no statistically significant difference between faster-acting insulin aspart and NovoRapid[®] in total glucose-lowering effect². Similar results were found in a clinical pharmacology trial in a CSII pump setting, where the difference in onset of exposure and early insulin exposure were even greater for faster-acting insulin aspart compared with NovoRapid® than observed for single dose s.c. injection $\frac{1}{2}$.

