3.2 Rationale for the trial

This trial aims to confirm the effect and to evaluate the safety of faster-acting insulin aspart with the use of CSII in adults with T1DM. In the European Medicines Agency (EMA) and FDA note for guidance on clinical investigation of medicinal products for the treatment of diabetes, HbA_{1c} is considered the most widely accepted measure of overall, long-term glucose control. Consequently, change from baseline in HbA_{1c} 16 weeks after randomisation will be included as the primary endpoint 16,17 .

The trial is intended to confirm that faster-acting insulin aspart, with a faster onset of action, is capable of demonstrating superior control of excessive postprandial glycaemic excursion during a standardised meal test and of demonstrating superiority of faster aspart in 1, 5-anhydroglucitol as another measure of PPG control, compared to NovoRapid[®].

The trial also aims to confirm superiority and investigate the differences in interstitial glucose (IG) of faster-acting insulin as compared to NovoRapid[®] based on data from continuous glucose monitoring (CGM) in adults with T1DM treated with CSII.

Further the trial is designed to confirm superiority of faster aspart in terms of overall glycaemic control measured as HbA_{1c} when compared to $NovoRapid^{®}$.

Protocol Trial ID: NN1218-3854 UTN: U1111-1118-2480 EudraCT no.: 2010-024054-11	CONFIDENTIAL	Date: Version: Status: Page:	04 February 2016 4.0 Final 23 of 149	Novo Nordisk
---------------------------------------------------------------------------------	--------------	---------------------------------------	-----------------------------------------------	--------------

The trial is a part of phase 3 clinical development program designed to meet the regulatory requirements for obtaining a CSII indication for faster-acting insulin aspart worldwide.

 Trial ID: NN1218-3854
 CONFIDENTIAL
 Version: 4.0

 UTN: U1111-1118-2480
 Status: Final

 EudraCT no.: 2010-024054-11
 Page: 24 of 149

4 Objectives and endpoints

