4.1.2 Secondary objectives

To confirm superiority of CSII treatment with faster-acting insulin aspart compared to CSII treatment with NovoRapid[®] in adults with T1DM, in terms of:

- Postprandial glucose regulation (meal test)
- Overall glycaemic control (HbA_{1c})
- Postprandial glucose excursions (1,5-anhydroglucitol)
- Time spent in low interstitial glucose (CGM)

To compare the effect and safety of CSII treatment with faster-acting insulin aspart vs. CSII treatment with NovoRapid[®] in adults with T1DM.

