More specifically the upper limit of the 95% confidence interval for the difference between faster-acting insulin aspart and NovoRapid[®] should be compared to a non-inferiority margin of 0.4%. If it is below or equal to 0.4% non-inferiority will be considered established and effect demonstrated.

The trial also aims to compare CSII treatment with faster-acting insulin aspart to NovoRapid[®] for a number of confirmatory secondary endpoints. The family-wise type I error rate will be controlled in the strong sense using a hierarchical (fixed sequence) testing procedure. This is based on a priority ordering of the null-hypotheses, and testing them in this order using the two-sided 95% confidence interval approach until an insignificant result appears. The effect is that rejection of a null hypothesis only will be considered for analyses where all previous null-hypotheses have been rejected in favour of faster-acting insulin aspart.

The steps in the hierarchical testing procedure are as follows:

- **Step 1 (Primary analysis)**: HbA_{1c} non-inferiority of faster-acting insulin aspart versus NovoRapid[®]
- **Step 2**: 1-hour PPG increment (meal test) superiority of faster-acting insulin aspart versus NovoRapid[®]
- **Step 3**: HbA_{1c} superiority of faster-acting insulin aspart versus NovoRapid[®]
- Step 4: 1,5-Anhydroglucitol superiority of faster-acting insulin aspart versus NovoRapid®
- **Step 5**: time spent in low IG (\leq 3.9 mmol/L [70 mg/dL]) superiority of faster-acting insulin aspart versus NovoRapid[®]

Primary estimand (de facto)

The primary estimand is defined as the treatment difference between Subjects randomised to CSII treatment with faster-acting insulin aspart and CSII treatment with NovoRapid $^{@}$ in adults with T1DM assessed by change from baseline in HbA $_{1c}$ 16 weeks after randomisation for all randomised Subjects regardless of treatment discontinuation or use of ancillary therapies. This estimand is a defacto estimand addressing effectiveness.

The primary estimand assesses the expected benefit that a Subject can achieve if prescribed to CSII treatment with faster-acting insulin aspart as compared to CSII treatment with NovoRapid[®] in adults with T1DM. By not putting any restrictions on the randomised treatment adherence, this

Protocol		Date:	04 February 2016	Novo Nordisk
Trial ID: NN1218-3854	CONFIDENTIAL	Version:	4.0	
UTN: U1111-1118-2480	CONFIDENTIAL	Status:	Final	

Page:

107 of 149

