17.1 Sample size calculation

The primary objective of the trial is to confirm the effect of CSII treatment with faster-acting insulin aspart in terms of glycaemic control by comparing it to CSII treatment with NovoRapid[®] in adults with T1DM, using a non-inferiority approach. The non-inferiority margin of 0.4% (absolute) was chosen as described in section 5.2.1. The statistical evaluation will be done as described in section 17.3.

The trial also aims to confirm superiority of CSII treatment with faster-acting insulin aspart for a number of secondary confirmatory endpoints using the hierarchical testing procedure as described in section 17 (General considerations).

The sample size is determined to ensure sufficient power for the first step and second step in the hierarchical testing procedure.

Protocol	Date:	04 February 2016	Novo Nordisk
Tain 1 ID. MNI1010 2054	Margian.	4.0	

 Trial ID: NN1218-3854
 CONFIDENTIAL
 Version: 4.0

 UTN: U1111-1118-2480
 Status: Final Page: 108 of 149

In previous exploratory trials where CSII treatment with faster aspart has been investigated, the completion rates have been high. Therefor it will not be unexpected that treatment discontinuation might be as low as 4% where trial discontinuation constitutes half of these.

The power for the non-inferiority step is based on a t-statistic under the assumption of a one-sided test of size 2.5 %. A mean treatment difference of -0.1% for the comparison between faster-acting insulin aspart and NovoRapid[®] is expected. As trials in this population where Subjects are using insulin pumps and where data from treatment withdrawn subjects is retrieved is limited, a conservative estimate of the standard deviation (SD) in change from baseline in HbA_{1c} of 0.8% was chosen.

For determination of power in the second step in the hierarchical testing, where change from baseline in 1-hour PPG increment 16 weeks after randomisation is compared between faster-acting insulin aspart and NovoRapid® a t-statistic with a two-sided test of size 5.0% is used, where the treatment difference is expected to be at least 0.9 mmol/L [16 mg/dL]. The SD=3.4 mmol/L [62 mg/dL] in change from baseline in 1-hour PPG increments 16 weeks after randomisation based on laboratory analysed PG in a standardised meal test will be considered reasonable, based on prior trials.

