For endpoints measured over time, mean values will be plotted to explore the trajectory over time. For survival endpoints (e.g. drop-out pattern) Kaplan-Meier plots are presented for each treatment.

Data collected before randomisation (Visit 6) will only be summarised descriptively.

Subjects that prematurely discontinue from treatment or withdraw from trial will attend end of treatment visits called visit 22A and 22B. Data collected at these visits will be reallocated to the next scheduled visit where the given assessment is planned. As a general rule, all observed values from randomised subjects will be used in all statistical analyses, but in case two different values are associated to the same visit in time, the use of a given value will depend on the estimand of interest. For the primary estimand the reallocated on-treatment value will not be used and for the secondary estimand the reallocated on-treatment value will be used. The estimands will be defined in the next section.

Testing strategy and estimands

The primary objective, to confirm the effect of CSII treatment with fast-acting insulin aspart in terms of glycaemic control by comparing it to CSII treatment with NovoRapid[®], in adults with T1DM, will be assessed by the change from baseline in HbA_{1c} using a non-inferiority approach.

More specifically the upper limit of the 95% confidence interval for the difference between fast-acting insulin aspart and NovoRapid[®] should be compared to a non-inferiority margin of 0.4%. If it is below or equal to 0.4% non-inferiority will be considered established and effect demonstrated.

The trial also aims to compare CSII treatment with fast-acting insulin aspart to NovoRapid[®] for a number of confirmatory secondary endpoints. The family-wise type I error rate will be controlled in the strong sense using a hierarchical (fixed sequence) testing procedure for the primary estimand. This is based on a priority ordering of the null-hypotheses, and testing them in this order using the two-sided 95% confidence interval approach until an insignificant result appears. The effect is that rejection of a null hypothesis only will be considered for analyses where all previous null-hypotheses have been rejected in favour of fast-acting insulin aspart.

The steps in the hierarchical testing procedure are as follows:

Step 1 (Primary analysis): HbA_{1c} non-inferiority of fast-acting insulin aspart versus NovoRapid[®]

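### Is it a flaw that 1,5-anhydroglucitol and time in low IG can be confirmed only after HbA1c superiority, a step with about 26% power at the plan's own inputs?

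*Protocol*

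**What the plan says.** Protocol section 17 (Estimands) and SAP section 2 (Testing strategy and estimands) set the same fixed sequence: HbA1c non-inferiority, 1-hour PPG increment, HbA1c superiority, 1,5-anhydroglucitol (1,5-AG), time in low IG. The protocol describes the procedure as "testing them in this order using the two-sided 95% confidence interval approach until an insignificant result appears". Each step uses the full two-sided 5% level, and the SAP states that "rejection of a null hypothesis only will be considered for analyses where all previous null-hypotheses have been rejected". No alpha is held back for Steps 4 and 5.

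Protocol 17.1 and SAP 2.1 limit the power claim: "The sample size is determined to ensure sufficient power for the first step and second step in the hierarchical testing procedure". Tables 17-2 and 2-2 therefore stop at Step 2. For HbA1c the planning values begin with "A mean treatment difference of -0.1% for the comparison between" the two insulins, with an SD of 0.8% that is called conservative.

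Protocol 4.1.2 lists all four superiority aims under one heading, "To confirm superiority of CSII treatment with faster-acting insulin aspart compared to CSII treatment with" NovoRapid. Protocol 3.2 names HbA1c, with reference to regulatory guidance, as the most widely accepted measure of long-term control and uses this to justify the primary endpoint. It describes 1,5-AG in terms "of demonstrating superiority of faster aspart in 1, 5-anhydroglucitol as another measure of PPG control".

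**The concern.** Two of the four superiority objectives sit behind a test that is likely to fail at the plan's own inputs. 1,5-AG is presented as a companion to the meal test, yet its confirmatory test depends on overall HbA1c superiority and not on the meal test alone. The documents' evidence on overall superiority is mixed. Protocol 3.1.2 says "Faster-acting insulin aspart also elicited a greater early glucose-lowering effect than" NovoRapid but reports no significant difference in total glucose-lowering effect. The same section reports a significantly larger HbA1c reduction in an earlier basal-bolus trial in type 1 diabetes.

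Protocol 3.2 also uses strong words: "Further the trial is designed to confirm superiority of faster aspart in terms of overall glycaemic control". Neither document shows the power for that claim.

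At stake is the confirmatory status of 1,5-AG and low IG. Both are analysed with 95% confidence intervals in any case. A procedure that reserves some alpha for 1,5-AG would let it be tested whenever the meal test succeeds, at an apparently small cost to HbA1c.

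**Working it through.** **Inputs (Protocol 17.1; SAP 2.1).** 225 per arm; Step 1 difference -0.1, SD 0.8, margin 0.4; Step 2 difference 0.9, SD 3.4; two-sided 5% (one-sided 2.5% for Step 1). Power comes from the noncentral t with 448 degrees of freedom and noncentrality difference / (SD × √(2/n)), where √(2/225) = 0.0943.

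**The plan's own figures.**
- Step 1: (0.4 + 0.1) / (0.8 × 0.0943) = 6.63, power above 99.9%, as stated.
- Step 2: 0.9 / (3.4 × 0.0943) = 2.81, power 80.0%, as stated.

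**Step 3.** 0.1 / (0.8 × 0.0943) = 1.33, power 26.2%. With smaller SDs, which are assumptions: 0.7 gives 32.7%, 0.6 gives 42.2%, 0.5 gives 56.2%.

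**Chance that Step 4 is reached under the plan.** If Steps 2 and 3 are independent: 0.800 × 0.262 = 21.0% at SD 0.8, and 0.800 × 0.562 = 45.0% at the assumed SD of 0.5. With an assumed correlation of 0.5: 25% and 51%.

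**Is the error control valid?** Yes. A false claim in a fixed sequence requires rejection of the first true null in the order, and that null is tested once at two-sided 5%. The family-wise rate cannot exceed this level, whatever the power of the steps.

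**What would a split buy?** Take 4% for HbA1c and 1% for 1,5-AG after Step 2, with alpha passed on after each rejection. Step 3 power becomes 23.2% (SD 0.8) or 52.5% (SD 0.5). Through Step 2 the HbA1c claim falls from 21.0% to 0.800 × 0.232 = 18.6%, or from 45.0% to 0.800 × 0.525 = 42.0%. Alpha passed back recovers part of this.

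Step 4 is then tested in 80.0% of trials. In 80.0 − 18.6 = 61.4% (SD 0.8) or 80.0 − 42.0 = 38.0% (SD 0.5) of trials it is tested at 1% only, so the share of trials in which it is tested does not compare like with like. The chance of a claim does. It was simulated with normal test statistics. The power of 1,5-AG at 5% has to be assumed, because the documents give neither effect nor SD for it:

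| HbA1c SD | Correlation | Assumed 1,5-AG power | 1,5-AG claim, plan → split |
|---|---|---|---|
| 0.8 | 0 | 30% | 6% → 13% |
| 0.8 | 0 | 50% | 11% → 26% |
| 0.8 | 0 | 80% | 17% → 51% |
| 0.5 | 0 | 30% | 14% → 17% |
| 0.5 | 0 | 50% | 23% → 31% |
| 0.5 | 0 | 80% | 36% → 56% |
| 0.5 | 0.5 | 30% | 22.9% → 23.9% |
| 0.5 | 0.5 | 80% | 46.9% → 60.4% |

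At SD 0.5, correlation 0.5 and 30% power, the HbA1c claim falls from 50.9% to about 48%. HbA1c thus loses about 3 points and 1,5-AG gains 1. With 30% power for low IG as well, its claim rate is 13.5% before and after. At 50% power, 1,5-AG gains about 4 points and HbA1c loses 2.5 to 2.9. With SD 0.8, independence and 80% power for both later endpoints, low IG rises from 13% to 33%.

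**The case for a change.** The strongest case for a change is that the arithmetic is right and the remedy is valid. At the only HbA1c inputs given, Step 4 stays closed in about four trials out of five. A 4%/1% split keeps family-wise control, needs no extra subjects or data, and more than doubles the chance of a 1,5-AG claim in every SD 0.8 row of the table. Step 3 power is not shown, and the verb in Protocol 3.2 promises more than 26% supports.

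The arithmetic stands. It does not show a defect:

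- The 26% uses an SD that the plan calls conservative, in an unadjusted t-test, while the planned analysis adjusts for baseline HbA1c and other factors. It is not a forecast.
- The gain is large only if the HbA1c SD is near 0.8 or 1,5-AG is well powered. Neither can be established from the documents.
- The cost falls on the endpoint that the protocol ranks higher. If HbA1c gave p between 0.04 and 0.05 and 1,5-AG p between 0.01 and 0.05, the fixed sequence would confirm both and the split neither.
- Steps 3 and 4 are decided by 95% confidence intervals. A split would need 96% and 99% decision intervals, or an interval that excludes zero could stand beside a failed claim.
- On wording, Protocol 17, 17.1 and 17.4.1 already describe the superiority comparisons as aims. Printing the Step 3 power would inform readers but change no result.

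**Conclusion.** The concern does not hold. The sequence is a declared order of priority with valid strong error control, the stated power figures reproduce, and both documents say that only Steps 1 and 2 were powered. Placing HbA1c superiority before a second postprandial measure is consistent with the weight that Protocol 3.2 gives to HbA1c, and postprandial control already has its own confirmatory test at Step 2.

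Step 3 power is 26.2% at the plan's inputs, and the chance of reaching Step 4 is then 21% (independence) to 25% (assumed correlation 0.5). Moving 1% of alpha to 1,5-AG would cost HbA1c 2.4 to 3.0 points under independence, before pass-back. In the scenarios tabulated it would gain 1,5-AG between 1 point and about 34 points (17% to 51%). That range rests on assumed values for the power of 1,5-AG, the correlation and the lower SD, so the documents cannot settle whether the exchange is worthwhile. Reasonable statisticians could choose either procedure. No rule, figure or conclusion in the plan is wrong because the sponsor chose the fixed sequence.

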17.1 Sample size calculation

The primary objective of the trial is to confirm the effect of CSII treatment with faster-acting insulin aspart in terms of glycaemic control by comparing it to CSII treatment with NovoRapid[®] in adults with T1DM, using a non-inferiority approach. The non-inferiority margin of 0.4% (absolute) was chosen as described in section 5.2.1. The statistical evaluation will be done as described in section 17.3.

The trial also aims to confirm superiority of CSII treatment with faster-acting insulin aspart for a number of secondary confirmatory endpoints using the hierarchical testing procedure as described in section 17 (General considerations).

The sample size is determined to ensure sufficient power for the first step and second step in the hierarchical testing procedure.

Protocol	Date:	04 February 2016	Novo Nordisk
Tain 1 ID. MNI1010 2054	Margian.	4.0	

 Trial ID: NN1218-3854
 CONFIDENTIAL
 Version: 4.0

 UTN: U1111-1118-2480
 Status: Final Page: 108 of 149

In previous exploratory trials where CSII treatment with faster aspart has been investigated, the completion rates have been high. Therefor it will not be unexpected that treatment discontinuation might be as low as 4% where trial discontinuation constitutes half of these.

The power for the non-inferiority step is based on a t-statistic under the assumption of a one-sided test of size 2.5 %. A mean treatment difference of -0.1% for the comparison between faster-acting insulin aspart and NovoRapid[®] is expected. As trials in this population where Subjects are using insulin pumps and where data from treatment withdrawn subjects is retrieved is limited, a conservative estimate of the standard deviation (SD) in change from baseline in HbA_{1c} of 0.8% was chosen.

For determination of power in the second step in the hierarchical testing, where change from baseline in 1-hour PPG increment 16 weeks after randomisation is compared between faster-acting insulin aspart and NovoRapid® a t-statistic with a two-sided test of size 5.0% is used, where the treatment difference is expected to be at least 0.9 mmol/L [16 mg/dL]. The SD=3.4 mmol/L [62 mg/dL] in change from baseline in 1-hour PPG increments 16 weeks after randomisation based on laboratory analysed PG in a standardised meal test will be considered reasonable, based on prior trials.

The power calculation is done using proc power in SAS Version 9.4. Please refer to Table 17–1 for assumption of the sample size calculation.

Table 17–1 Specifications assumed for sample size calculation

	Statistical	Significance	Analysis	Non-inferiority	SD.	Mean	Randomisation
	test	Level	Population	Margin	SD	Difference	Scheme
Step 1	2-group t-test	One-sided 2.5%	FAS	0.4% (absolute)	0.8	-0.1	1:1
Step 2	2-group t-test	Two-sided 5.0%	FAS	NA	3.4	0.9	1:1

Protocol	Date:	04 February 2016	Novo Nordisk

Trial ID: NN1218-3854
UTN: U1111-1118-2480
EudraCT no.: 2010-024054-11

CONFIDENTIAL

CONFIDENTIAL

Version: 4.0
Status: Final
Page: 109 of 149

In Table 17–2, the sensitivity of the sample size to the power in Step 1 and Step 2 is shown for three different sizes of FAS. Three different choices of the mean difference are used to calculate the power in Step 2.

Table 17–2 Sensitivity of sample size to power in step 1 and step 2

		Step 1			Step 2	2		
N Total	N per arm	Mean		Step 1 Power	Null	Mean	l	Step 2 Power
FAS	FAS	Diff	SD	(%)	Diff	Diff	SD	(%)
		-0.1	0.80	>99.9	0	0.8	3.4	52.8
300	150	-0.1	0.80	>99.9	0	0.9	3.4	62.7
		-0.1	0.80	>99.9	0	1.0	3.4	71.9
		-0.1	0.80	>99.9	0	0.8	3.4	70.2
450	225	-0.1	0.80	>99.9	0	0.9	3.4	80.0
		-0.1	0.80	>99.9	0	1.0	3.4	87.6
		-0.1	0.80	>99.9	0	0.8	3.4	82.0
600	300	-0.1	0.80	>99.9	0	0.9	3.4	89.9
		-0.1	0.80	>99.9	0	1.0	3.4	94.9

In conclusion, with 450 Subjects in the FAS (225 Subjects per group) will ensure a power of >99.9% to conclude HbA_{1c} non-inferiority in the first step. This sample size gives 80.0% marginal power to conclude 1 hour PPG increment superiority in the second step.

Assuming a screening failure rate of 24% and run-in failure rate of 11%, 666 Subjects should be screened for inclusion in the trial.

17.2 Definition of analysis sets

The following analysis sets are defined in accordance with the ICH-E9 guidance 1 :

 Trial ID: NN1218-3854
 Version:
 4.0

 UTN: U1111-1118-2480
 Status:
 Final

 EudraCT no.: 2010-024054-11
 Page:
 110 of 149

• Full Analysis Set (FAS) includes all randomised Subjects. In exceptional cases, randomised Subjects may be excluded from the FAS. In such cases, the reason for exclusion will be justified and documented. Subjects in the FAS will contribute to the evaluation "as randomised"

- Per Protocol (PP) Analysis Set includes all Subjects in the full analysis set, excluding Subjects who:
 - Have violated any inclusion criteria
 - Have fulfilled any exclusion criteria

Subjects in the PP set will contribute to the evaluation "as treated"

• Safety Analysis Set includes all Subjects receiving at least one dose of the IMP or its comparator. Subjects in the safety analysis set will contribute to the evaluation "as treated".

Randomised Subjects who are lost to follow-up, and where no exposure information of the trial product or its comparator is available after randomisation, will be handled as unexposed.

Before data are released for statistical review, a blinded review of all data will take place to identify serious non-adherence to the protocol that may potentially affect the results. Furthermore, extreme values and outliers will be identified by the statistician during programming and data review, according to ICH-E9¹. This will be performed by using a fake randomisation.

The Subjects or observations to be excluded, and the reasons for their exclusion must be documented and signed by those responsible before database lock. The Subjects and observations excluded from analysis sets, and the reason for this, will be described in the clinical trial report (CTR).

